4.1.2 Premature permanent discontinuation of study medication

Discontinuation from study medication is not the same as withdrawal from the study. As described in Section 5.8.3 in the CSP there are several options for continuation in the study.

It is expected that complete information on the primary composite endpoint event (and as much as possible of the eCRF data for patients contacted by telephone) will be obtained for all patients who prematurely discontinue study medication, unless they refuse any form of follow-up and withdraw consent or are LTFU. Thus, event free patients who prematurely permanently discontinue study medication will in general not be censored before PACD in the primary ITT analysis.

4.1.3 Investigation of informative censoring

The time-to-event analysis (Cox regression) relies on the assumption of non-informative censoring.

Sensitivity analyses to assess possible effects of informative censoring on the primary endpoint event are described in Section 4.1.1 and Section 4.2.1.1.

4.2 Analysis methods

4.2.1 Primary efficacy variable

The primary efficacy variable, time from randomisation to the first occurrence of any event from the composite of CV death, MI and stroke, will be analysed using the methodology described in Section 4.1. The null hypothesis of no treatment effect,

H_0 : $HR(\text{ticagrelor divided by placebo}) = 1$,

versus the alternative hypothesis,

H_1 : $HR \neq 1$,

will be tested at 4.96% two-sided significance level to account for the planned interim analyses with the overall type I error preserved at 5% (see Section 5).

4.2.1.1 Model checking and sensitivity analyses

The assumption of proportional hazards for the factor for treatment group will be assessed visually using log-cumulative hazard plots. The effect of any departures from proportional hazards will be discussed as part of the presentation of results of the analyses.

To assess possible effects of missing data, sensitivity analyses will be done as follows. The event rate in the placebo arm will be used to estimate the intensity of a Poisson process. Based on the missing follow-up time, i.e. the time from censoring to PACD, the expected number of events in the ticagrelor group that could have been observed if the patients had completed the study will be estimated from the Poisson process. The comparison of ticagrelor and placebo will be recalculated with these additional events. If the result is still significant with these additional events, the minimum intensity of the Poisson process that on average gives non-significant results when adding events to the ticagrelor group will be estimated using simulations.

Sensitivity analysis of the primary composite endpoint event will also include analysis

- Including vital status information from patients who have withdrawn consent, where deaths are assumed to be CV deaths
- Including events that occur after PACD but before SCV (i.e. patients who have not had the events will be censored at the earlier of the SCV date, last study contact when all components were assessed or date of death from non-CV causes)
- With a Wei-Lin-Weissfeld model for recurrent event analysis of the events in the primary composite endpoint (Wei 1989), where 3 are the maximum number of events
- With a Lin-Wei-Yang-Ying model for recurrent event analysis of the events in the primary composite endpoint (Lin 2000)
- On treatment, where patients who have not had a primary event will be censored 3, 7 and 30 days after last dose of study drug, respectively
- With events as reported by the investigator
- With treatment and Reduction of Atherothrombosis for Continued Health (REACH) risk score for secondary CV events as covariates in a Cox proportional hazards model (Wilson 2012)
- With treatment and a risk factor as explanatory variables in a Cox proportional hazards model, for the risk factors systolic blood pressure, diastolic blood pressure, pulse pressure and heart rate at baseline, respectively
- With treatment and duration of diabetes (continuous) as explanatory variables in a Cox proportional hazards model.

The proportion of patients with complete follow-up will be presented per treatment group. Patients for whom all components of the primary endpoint event have been ascertained on or after PACD are considered to have complete follow-up.

To explore the consistency between the treatment effect of ticagrelor 60 mg and the overall treatment effect of ticagrelor, a sensitivity analysis of the primary efficacy variable with a Cox proportional hazards model with time dependent covariates will be performed. In this model a factor for treatment group and a time dependent indicator of the dose of study drug for patients treated with ticagrelor are included as covariates. The model can be written:

$$h(t, x_1, x_2(t))=h_0(t)\exp\{\beta_1\cdot x_1+\beta_2\cdot x_2(t)\}$$

where $h_0(t)$ is the baseline hazard, β_1 is the coefficient for treatment group, x_1 is defined as 0 for placebo and 1 for ticagrelor, β_2 is the coefficient for the time dependent study drug dose variable for ticagrelor and $x_2(t)$ is equal to 1 if the patient is treated with ticagrelor 60 mg at time t and otherwise equal to 0. Thus, the hazard ratio of ticagrelor 60 mg versus placebo is $\exp\{\beta_1+\beta_2\}$.

Further sensitivity analysis of the consistency of treatment effect for the 60 mg dose compared to the overall treatment effect will be performed by assessing the effect in patients randomised to ticagrelor 60 mg compared to those randomised to ticagrelor 60 mg placebo.

Sensitivity analysis of the primary composite endpoint event will also include analysis on-treatment in patients randomised ticagrelor 60 mg or ticagrelor 60 mg placebo and in patients randomised to ticagrelor 90 mg or ticagrelor 90 mg placebo, respectively. The treatment effect of the randomised dose of ticagrelor versus the randomised dose of ticagrelor placebo will be estimated with a Cox proportional hazards model with treatment as the only explanatory variable. Events that occur up to and including 7 days after last randomised dose of study drug will be included in the analysis, and event free patients will be censored at the earlier of 7 days after last randomised dose of study drug, last contact, non-CV death, SCV or withdrawal of consent.

A landmark analysis of the primary composite endpoint to explore the consistency of treatment effect over treatment dose will be performed. In the analysis, the incidence of primary composite events when the patients are treated with ticagrelor 90 mg or ticagrelor 90 mg placebo, and when patients are treated with ticagrelor 60 mg or ticagrelor 60 mg placebo for patients who were event free up to the day of the first 60 mg dose are examined.

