12.2.1.1 Primary efficacy variable

The primary efficacy variable, time from randomisation to the first occurrence of any event from the composite of CV death, MI or stroke, will be analysed using the methodology described in Section 12.2.1. The null hypothesis of no treatment effect,

H_0 : HR (ticagrelor divided by placebo) = 1,

vs. the alternative hypothesis,

H_1 : HR \neq 1,

will be tested at 4.96% two-sided significance level.

The assumption of proportional hazards will be assessed visually using log-cumulative hazard plots. The effect of any departures from proportional hazards will be discussed as part of the presentation of results.

To assess possible effects of missing data, sensitivity analyses will be done as follows. The event rate in the placebo arm will be used to estimate the intensity of a Poisson process. Based on the missing follow-up time, i.e. the time from censoring to PACD, the expected number of events in the ticagrelor group that could have been observed if the patients had completed the study will be estimated from the Poisson process. The comparison of ticagrelor and placebo will be recalculated with these additional events. If the result is still significant with these additional events, the intensity of the Poisson process will be increased and events will be added to the ticagrelor group until the primary analysis is non-significant.

Subgroup analyses on the primary efficacy variable will be performed to evaluate variation of treatment effect. Relevant subgroups, eg age, sex, race, ASA use and medical history, will be examined. Hazard ratios and 95% confidence intervals will be reported for each subgroup as well as p-values for the tests of interaction between treatment and each subgroup.

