12.2.4 Censoring

The EC will monitor the accrual of the number of primary events and when appropriate predict and define a PACD at which time the pre-defined target number of events for the primary composite endpoint are expected to have occurred.

The PACD will be the common date at which all patients who are event free for the given endpoint and have not withdrawn consent for participating in the study will be censored in efficacy time-to-event analyses. Events that occur after the PACD but before the SCV will also be collected and adjudicated. These events will be included in sensitivity analyses but not in the primary analysis.

Patients who have not had the event(s) in question will be censored at the earlier of (1) the PACD and (2) the last study contact when all components of the endpoint in question were assessed. In the analysis of CV death and composites including CV death censoring will occur at the earliest of (1), (2) and (3) the date of death from non-cardiovascular causes. For endpoints not including death, all deaths are censoring events. In safety time-to-event analysis of bleeding, patients not having suffered any bleeding event in the given category will be censored at the earlier of SCV, 7 days after last dose of study drug, death, last contact or withdrawal of consent.

Complete endpoint information will be pursued with every effort for all patients regardless of their study medication status, unless they exercise their right to withdraw consent. Patients

who have a non-fatal event will continue study follow-up. For patients who withdraw consent and for whom only vital status (known to be alive at study closure, or date of death) may be obtained from public records, the occurrence of all components of the primary endpoint cannot be assessed. Thus, in the main analyses patients will be censored at the time of consent withdrawal. However, the determination of all-cause death will utilise all publicly known mortality data, even that extending beyond date of consent withdrawal. The vital status information will be included in the analysis of all cause death as a single endpoint, in sensitivity analysis and tabulations.

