4.1.1 Censoring

The executive committee will monitor the accrual of the number of primary events and when appropriate predict and define a primary analysis censoring date (PACD) at which time the pre-defined target number of events for the primary composite endpoint are expected to have occurred.

The PACD will be the common date at which all patients who are event free for the given endpoint and have not withdrawn consent for participating in the study will be censored in efficacy time-to-event analyses. Events that occur after the PACD but before the SCV will also be collected and adjudicated. These events will be included in sensitivity analyses but not in the primary analysis. Events that occur after SCV will be described in text or tabulated descriptively.

Patients who have not had the event(s) in question will be censored at the earlier of (1) the PACD and (2) the last study contact when all components of the endpoint in question were assessed. In the analysis of CV death and composites including CV death censoring will occur at the earlier of (1), (2) and (3) the date of death from non-cardiovascular causes. For endpoints not including death, all deaths are censoring events.

Complete endpoint information will be pursued with every effort for all patients regardless of their study medication status, unless they exercise their right to withdraw consent. Patients who have a non-fatal event will continue study follow-up. For patients who withdraw consent and for whom only vital status (known to be alive at study closure, or date of death) may be obtained from public records, the occurrence of all components of the primary endpoint cannot be assessed. Thus, in the main analyses patients will be censored at the time when all elements of the endpoint were assessed for those patients who withdraw consent and for whom only vital status is known from public records. However, the determination of all-cause death will utilise all publicly known mortality data, even that extending beyond date of consent withdrawal. The vital status information will be included in the analysis of all-cause death as a single endpoint, and in sensitivity analysis and tabulations.

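### The Poisson missing-data analysis counts time after a known non-CV death as missing follow-up, so its tipping intensity cannot be read as a rate for patients whose follow-up is truly missing

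*SAP*

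**What the plan says.** SAP 4.2.1.1 and Protocol 12.2.1.1 describe the same two-step analysis. The placebo event rate sets the intensity of a Poisson process, which is applied to the missing follow-up time, in the SAP's words "i.e. the time from censoring to PACD, the expected number of events in the ticagrelor group that could have been observed". The protocol has the same definition: "Based on the missing follow-up time, i.e. the time from censoring to PACD, the expected number of events in the ticagrelor group". The quantity sought is "the expected number of events in the ticagrelor group that could have been observed if the patients had completed the study".

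If the comparison is still significant with these events added, the SAP's second step estimates "the minimum intensity of the Poisson process that on average gives non-significant results when adding events to the ticagrelor group". The protocol instead raises the intensity until significance is lost.

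The time base depends on the censoring rule. For composites that include CV death, SAP 4.1.1 states that "censoring will occur at the earlier of (1), (2) and (3) the date of death from non-cardiovascular causes", where (1) is PACD and (2) is the last contact at which all components were assessed. Protocol 12.2.4 has the same rule: "censoring will occur at the earliest of (1), (2) and (3) the date of death from non-cardiovascular causes". SAP 4.2.1.1 itself treats non-CV death as a censoring date in the analysis that runs to the study closure visit: "last study contact when all components were assessed or date of death from non-CV causes". The Poisson text makes no exception for these patients.

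**The concern.** A patient who dies of a non-CV cause before PACD, free of a primary event, is censored at death. Under the stated definition, the time from that death to PACD is missing follow-up. Primary events are then imputed to it, first at the placebo rate and then at the tipping intensity. Yet the outcome of such a patient is fully known, and no primary event can follow.

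What is at stake is how the second step is read. A reader will ask whether the tipping intensity is plausible for patients who withdrew consent or were lost. If much of the time base belongs to the dead, the tipping events are spread over more person-time than is really missing, and the intensity comes out too low for that question. The plan expects negligible loss to follow-up (SAP 1.3), so truly missing time may be small and post-death time may dominate.

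**Working it through.** **Inputs from the documents** (SAP 1.3 and 4.2.1): 19000 patients at 1:1, so 9500 per arm; mean follow-up 40 months (F = 3.333 years, treated as fixed); placebo rate 0.025 per year; HR 0.84, so ticagrelor rate 0.021; 1385 events; two-sided alpha 0.0496 (critical z 1.963).

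**Assumptions, because the documents give no figure:** non-CV death 0.5, 1.0 or 1.5% per year; withdrawal or loss 0.25 to 2% per year; constant hazards.

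**1. The plan's own figure.** 4(1.963 + 1.282)²/(ln 0.84)² = 1385.5, and 1385 events give power 0.900. The stated event number reproduces. The documents give no figure for the Poisson analysis.

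**2. Events needed to lose significance.** At an observed HR of 0.84 the split is 1385 × 0.84/1.84 = 632.3 ticagrelor and 752.7 placebo events. SE = √(1/632.3 + 1/752.7) = 0.0539, z = −3.23, p = 0.0012. Solving ln((632.3 + K)/752.7) = −1.963·√(1/(632.3 + K) + 1/752.7) gives K = 46.1 added ticagrelor events, if no risk time is added with them.

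**3. Post-death time.** With non-CV death hazard m and L = 0.021 + m:

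- deaths while event-free = 9500·(m/L)·(1 − e^(−LF))
- post-death person-years D = 9500·m·[F/L − (1 − e^(−LF))/L²]
- observed person-years B = 9500·(1 − e^(−LF))/L

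| Assumed m per year | Deaths | D | B | Events added at 0.025 | Share of K |
|---|---|---|---|---|---|
| 0.5% | 152 | 256 | 30,333 | 6.4 | 14% |
| 1.0% | 301 | 510 | 30,085 | 12.8 | 28% |
| 1.5% | 448 | 761 | 29,840 | 19.0 | 41% |

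**4. First step, effect of post-death time alone.** Adding events only, HR = (632.3 + added)/752.7 = 0.849 to 0.865, p = 0.0023 to 0.0068. Adding the risk time too multiplies the HR by B/(B + D), giving 0.841 to 0.844, p = 0.0013 to 0.0015. Significance holds in every case.

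**5. Second step, tipping intensity.** Let M be truly missing ticagrelor person-years.

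- Events only: K/(M + D) is reported and K/M is wanted. The ratio is M/(M + D), whatever the value of K.
- Risk time added: for imputed time T, solve ln[((632.3 + λT)/752.7)·B/(B + T)] = −1.963·√(1/(632.3 + λT) + 1/752.7) for λ, with T = M + D (reported) or T = M (wanted).

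Illustration with M equal to D:

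| M = D | Events only: reported / wanted | Ratio | Risk time added: reported / wanted | Ratio |
|---|---|---|---|---|
| 256 | 0.090 / 0.180 | 50% | 0.113 / 0.203 | 56% |
| 510 | 0.045 / 0.090 | 50% | 0.068 / 0.114 | 60% |
| 761 | 0.030 / 0.061 | 50% | 0.054 / 0.084 | 64% |

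**6. Away from M = D.** With withdrawal hazard w and h = 0.021 + w + m, M and D are 9500·w and 9500·m times [F/h − (1 − e^(−hF))/h²], so the events-only ratio is w/(w + m). For w = 0.5% and m = 1.0%, M = 254 and D = 507. The reported rate is 0.061 against 0.182 (33%) with events only, and 0.084 against 0.205 (41%) with risk time.

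Over the whole assumed grid, the events-only ratio runs from 0.0025/0.0175 = 14% to 0.020/0.025 = 80%. With risk time (taking B at L = h) it runs from 0.0756/0.388 = 19% to 0.0605/0.0697 = 87%. One simulated trial analysed by Cox regression (HR 0.838, 1349 events, w = 0.5%, m = 1.0%) gave about 0.09 against 0.25. The direction is always the same.

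**The case against.** The strongest defence is that the inclusion is deliberate. SAP 4.2.1.1 counts follow-up as complete only if all components were ascertained on or after PACD, with no exception for non-CV death. The March 2017 entry in the amendment history shows that this was a conscious change. SAP 4.1.3 also refers to 4.2.1.1 for the effect of informative censoring, and censoring at non-CV death is one place where that assumption could fail. On this view the analysis stress-tests all early censoring against ticagrelor, and the tipping intensity correctly answers the question set.

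This has weight. A reader might infer that the SAP contradicts its own stated aim. The documents do not establish that, because completing the study can be read as a hypothetical covering everyone censored before PACD. But no passage says why primary events should be imputed after death in an analysis introduced as addressing missing data. A single rate pooled over dead and lost patients is also not interpretable for either group.

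A second objection concerns size, and it stands. The share-of-margin figures and the 50% ratio hold only if events are added without risk time. The SAP does not say which is done, but the comparison is a Cox model, which needs a time for each added event. With risk time added, the first step barely moves and the dilution is smaller.

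Third, non-CV death is partly covered elsewhere: all-cause death is a secondary variable, the composite of all-cause death, MI or stroke is exploratory, and deaths after withdrawal are counted as CV deaths in one sensitivity analysis. None of these gives a tipping intensity.

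**Conclusion.** Wrong as written, minor severity. Following the stated definition imputes primary events to ticagrelor patients known to be dead. The tipping intensity is then lower than the rate that truly missing follow-up would need in order to overturn the result.

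If truly missing and post-death time are equal, the reported intensity is about 50% of the corrected one with events only, and about 56-64% with risk time added (assumed non-CV death 0.5-1.5% per year). Equality is itself an illustration. The true ratio depends on non-CV death and withdrawal rates that the documents do not give.

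A reader might go further and infer that the primary conclusion or the type I error is at risk, or that the drug is favoured. The documents do not support this. The error is conservative, no decision rule uses the intensity, and the second step runs only if significance survives the first. At the planning HR of 0.84, post-death time alone does not remove significance in the first step.

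**What to change.** In SAP 4.2.1.1, define missing follow-up as the time from the last complete endpoint assessment to the earlier of PACD and any known death. Restrict it to event-free patients censored early for reasons other than death.

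State whether imputed risk time is added along with the events. Report the imputed person-years by arm and by reason for censoring. If a stress test of non-CV death as informative censoring is wanted, run it as a separate, labelled analysis.

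Record the departure from Protocol 12.2.1.1 in SAP Section 6, which exists for such changes; no protocol amendment is needed for this alone. The cost is one redefined sentence, a line in Section 6 and a small table. No new data are needed, because the censoring rules already use the date of death.

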5.5.2.1 Dose Switch strategy

When the new study medication comprising of ticagrelor 60 mg or corresponding placebo is locally available at study site, patients already randomized to ticagrelor 90 mg or corresponding placebo will be switched to the new study medication at the next planned visit.

The dose switch must occur on an on-site visit. If the next planned visit is a scheduled telephone contact (e.g. Visit 3, 4, 7, 9, 11, 13 etc.), the patient must be re-scheduled to come in for an on-site visit. By following this strategy all patients at a study site that currently are treated with ticagrelor 90 mg or corresponding placebo, will be switched to the new medication (ticagrelor 60 mg or corresponding placebo) within a 3 months period counted from when the new study medication is available at site.

At the discretion of the PI, an additional visit can be scheduled to allow for a dose switch ahead of next planned visit.

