5.5.3 Development of indication for ADP receptor antagonist during study

If a patient randomised to study medication develops an indication for use of an ADP receptor antagonist according to medical guidelines (eg, an ACS or PCI), selection of the appropriate agent for individual patients is at the discretion of the investigator or treating physician and should be made in accordance with local medical guidelines and standard of care.

The patient must temporarily stop study medication during the open-label therapy with the ADP receptor antagonist. Patients should return to randomised treatment (ticagrelor or placebo) when there is no longer an indication for ADP receptor antagonist therapy according to medical guidelines.

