Similarly, complete information on the primary endpoint may not be obtained for patients who are lost to follow-up (LTFU). Any such patient will be censored in the analysis of the primary composite endpoint at the last contact where all elements of the endpoint were assessed. A patient will not be recorded as LTFU until the end of the study, after every allowable effort to get in contact has been made. Hence, it is anticipated that the number of patients LTFU will be limited.

In safety time-to-event analysis of bleeding and discontinuation of study drug due to bleeding, patients not having suffered any bleeding event in the given category will be censored at the earlier of SCV, 7 days after last dose of study drug, death, last contact or withdrawal of consent.

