4.2.6.2 Time to event analysis of bleedings

Time to bleeding event variables will be analysed using the same methodology as for the efficacy variables as described in Section 4.1.

Explorative analysis of time to bleeding for selected subgroups will be performed for the main bleeding categorisations (TIMI major, TIMI major or minor, and PLATO major). Subgroups will be the groups defined for the efficacy analysis in Section 4.2.1.2.

Sensitivity analysis of TIMI major bleeding to address the consistency of the overall effect of ticagrelor on bleeding compared to the 60 mg dose will be performed with a Cox proportional hazards model with time dependent covariates, as described in Section 4.2.1.1 for the primary variable.

Furthermore, a sensitivity analysis of TIMI major bleeding on-treatment in patients randomised to ticagrelor 60 mg or ticagrelor 60 mg placebo and in patients randomised to ticagrelor 90 mg or ticagrelor 90 mg placebo will be performed. These analyses include events that occur up to and including 7 days after last randomised dose of study drug, and event free patients will be censored at the earlier of 7 days after last randomised dose of study drug, last contact, death, SCV or withdrawal of consent.

A landmark analysis of TIMI major bleeding to explore the consistency of treatment effect over treatment dose will be performed. In the analysis, the incidence of TIMI major bleedings

when the patients are treated with ticagrelor 90 mg or ticagrelor 90 mg placebo, and when patients are treated with ticagrelor 60 mg or ticagrelor 60 mg placebo for patients who were event free up to the day of the first 60 mg dose are examined.

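### The time-dependent dose model sets on-drug 60 mg time against all placebo time, so its 60 mg versus placebo hazard ratio is not like for like

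*SAP*

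**What the plan says.** The stated aim in SAP 4.2.1.1 is "To explore the consistency between the treatment effect of ticagrelor 60 mg and the overall treatment effect of ticagrelor". The model is h0(t)·exp{β1·x1 + β2·x2(t)}. Here x1 is the randomised arm (0 placebo, 1 ticagrelor), and x2(t) "is equal to 1 if the patient is treated with ticagrelor 60 mg at time" t and is 0 in every other case. The SAP then concludes: "Thus, the hazard ratio of ticagrelor 60 mg versus placebo is" exp(β1+β2).

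The model has no off-drug term, no dose-period term for placebo and no on-treatment censoring. SAP 2.1.1 analyses efficacy in the FAS by randomised arm and counts events after stopping as well as before. SAP 4.1.2 adds that "event free patients who prematurely permanently discontinue study medication will in general not be censored before PACD in the primary ITT analysis".

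SAP 4.2.6.2 reuses the model for TIMI major bleeding, which "will be performed with a Cox proportional hazards model with time dependent covariates, as described in Section 4.2.1.1". For bleeding, however, SAP 4.1.1 says that patients without an event "will be censored at the earlier of SCV, 7 days after last dose of study drug, death, last contact or withdrawal of consent".

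**The concern.** Read as written, the coding sorts follow-up as follows.

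| Follow-up time | x1 | x2(t) | Hazard ratio against placebo |
|---|---|---|---|
| Placebo, on or off drug | 0 | 0 | 1 (reference) |
| Ticagrelor, on 60 mg | 1 | 1 | exp(β1+β2) |
| Ticagrelor, on 90 mg | 1 | 0 | exp(β1) |
| Ticagrelor, off drug | 1 | 0 | exp(β1) |

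Off-drug time is removed from the 60 mg side of exp(β1+β2) and kept on the placebo side. The overall hazard ratio it is meant to be checked against keeps off-drug time in both arms. A gap between the two can therefore appear when both doses have exactly the same effect. It could also put this model at odds with the two-arm dose analyses in the same section for reasons unrelated to dose.

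Off-drug time is not a random sample of follow-up. Protocol 5.5.3 gives one reason: "The patient must temporarily stop study medication during the open-label therapy with the ADP receptor antagonist". Protocol 5.8.1 adds major bleeding, surgery and prohibited medication.

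A lesser point is that exp(β1) mixes 90 mg time with off-drug time and must not be read as 90 mg versus placebo. The SAP does not claim that it is.

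**Working it through.** **Plan's own figures.** The SAP gives no number for this model. Its design figure reproduces: 4(1.963 + 1.282)²/(ln 0.84)² = 42.12/0.0304, or 1386 events against the stated 1385, with power 89.99%. That calculation is not affected by this point.

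**Inputs from the documents (SAP 1.3):** placebo rate 2.5% a year, average follow-up T = 40/12 = 3.33 years, 1:1 allocation, assumed hazard ratio 0.84.

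**Assumptions, because the documents give no figures:** permanent stopping at λ = 5, 10 or 15% a year, equal in both arms and without restart; off-drug hazard k times the on-placebo hazard in both arms, with k from 0.8 to 2.0.

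**Step 1: off-drug share of placebo follow-up.** f = 1 − (1 − e^(−λT))/(λT).
- λ = 5%: λT = 0.167, f = 8%
- λ = 10%: λT = 0.333, f = 15%
- λ = 15%: λT = 0.5, f = 21%

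**Step 2: drug with no effect.** The average placebo hazard is the on-placebo hazard times (1 − f) + kf, so exp(β1+β2) ≈ 1/(1 + f(k − 1)).

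| f | k = 0.8 | k = 1.0 | k = 1.5 | k = 2.0 |
|---|---|---|---|---|
| 0.08 | 1.016 | 1.000 | 0.962 | 0.926 |
| 0.15 | 1.031 | 1.000 | 0.930 | 0.870 |
| 0.21 | 1.044 | 1.000 | 0.905 | 0.826 |

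Fitting the SAP model to expected events (3-month bands, 28-month enrolment, changeover to 60 mg assumed at month 18) gives 0.960, 0.930 and 0.905 at k = 1.5, and 0.924, 0.870 and 0.828 at k = 2. Moving the changeover from month 15 to month 24 shifts the 10%, k = 1.5 value only from 0.932 to 0.922.

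**Step 3: true on-drug hazard ratio 0.84 at both doses.** The model gives 0.84/(1 + f(k − 1)). The ITT value is [0.84(1 − f) + kf]/[(1 − f) + kf].
- k = 1: the model gives 0.84. The ITT value is 0.84 + 0.16f = 0.853, 0.864 and 0.874 for f = 0.08, 0.15 and 0.21.
- k = 1.5, f = 0.15: the model gives 0.84/1.075 = 0.781 (fitted 0.780). The ITT value is (0.714 + 0.225)/1.075 = 0.873.

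**Step 4: simulated Cox models.** The runs used 19000 patients, 10% a year stopping and 30% of patients starting on 90 mg. With no drug effect, exp(β1+β2) was 0.93, 0.87 and 0.77 at k = 1.5, 2 and 3. At k = 1.5 and 2 the upper 95% limit fell below 1 in about 29% and 80% of trials, against about 2% when on/off-drug status was coded in both arms. These runs averaged about 1750 and 1869 events rather than stopping at 1385, so the two frequencies are somewhat high for this trial. exp(β1) was 1.28 and 1.52 under the same null.

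**Step 5: source of the distortion.** Adding an off-drug term in the ticagrelor arm alone moves the 10%, k = 1.5 null value from 0.930 to 0.931. The one-sided placebo reference drives the error in the sum, not the pooling of off-drug time with 90 mg.

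**The case against.** **Another reading of x2(t).** The SAP introduces the covariate as an indicator of dose, and the FAS is by randomised arm. If x2 stays at 1 after stopping, both arms follow a treatment policy. The wording of treatment at time t, and 0 otherwise, points the other way. Even under simple carry-forward, the null value at k of 1.5 to 2 is about 0.976 to 0.994. The reason is that ticagrelor patients who stop while on 90 mg never reach x2 = 1, while their placebo counterparts stay in the reference.

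**The open-label ADP antagonist example.** This is a time-to-first-event analysis, so a patient whose ACS is an adjudicated MI has already left the risk set. The remaining open-label time is under active antiplatelet treatment and may carry lower risk. This stands: the provision shows that off-drug time is selected, but it does not support k above 1. The calculation also models permanent stopping, whereas the protocol wants study drug restarted where possible.

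**Size is assumed.** This is true. At k = 1 the gap is ordinary dilution, and the largest, ln(0.874/0.84) = 0.040, is below the standard error of about 2/√1385 = 0.054. But the SAP presents the two figures as a consistency check, and the gap is systematic.

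**Other analyses cover dose.** SAP 4.2.1.1 also has a comparison by randomised 60 mg, a 7-day on-treatment analysis and a landmark analysis, all two-arm. That limits the harm. It does not make the label on this model correct.

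**Bleeding.** The 7-day rule in SAP 4.1.1 largely removes permanent off-drug time. Temporary interruptions remain open.

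**Conclusion.** The concern holds. It follows from the formula and the follow-up rules that exp(β1+β2) compares on-60-mg ticagrelor time with all placebo time; no assumption is needed for that.

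The size and direction do rest on assumptions. If off-drug risk exceeds on-placebo risk, 60 mg looks better than it is; if it is lower, worse. Over 5 to 15% a year stopping, a null drug would show 0.960 to 0.905 at 1.5 times and 0.924 to 0.828 at 2 times, no shift at equal risk, and 1.02 to 1.04 at 0.8 times. Even at equal risk, the model and the ITT estimate differ (0.84 against 0.853 to 0.874) when the doses do not.

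This is an exploratory sensitivity analysis. The primary test, the alpha and the sample size are unaffected. It should still be corrected, because the output would be labelled as the effect of the dose the trial adopted.

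**What to change.** Define the dose period in both arms, treat off-drug time the same way in each, and label the estimate accordingly. There are two options.

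1. **ITT-type contrast (preferred, because the comparison is with the overall ITT effect).** The 60 mg period starts at randomisation for patients randomised to 60 mg or its placebo. For the others it starts at the first planned visit after 60 mg supply reached the site, following Protocol 5.5.2.1, under which patients "will be switched to the new study medication at the next planned visit". Apply this to every patient in both arms, on or off drug, and carry it forward after stopping. Fit arm, period and arm × period. A few early switches at the investigator's discretion will be slightly misdated.
2. **On-treatment contrast.** Censor both arms at the same interval after last dose and handle temporary interruptions alike.

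With no drug effect and equal stopping, both options return 1.000. With a true 0.84, 10% a year and k = 1.5, option 1 gives 0.875 (ITT 0.873) and option 2 gives 0.840. With stopping at 10% a year on ticagrelor and 7% on placebo, no drug effect and k = 1.5, the SAP coding gives 0.948, ITT 1.019, option 1 1.021 and option 2 1.000.

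For TIMI major bleeding, state that the 7-day censoring applies to this model and how interruptions are coded in both arms. The landmark analysis needs no change.

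The cost is SAP wording and one recoded covariate, with no new patient data. Option 1 needs a 60 mg supply date per site. The documents do not say one is recorded, but the first 60 mg kit allocated at the site through IVRS/IWRS could serve. Option 2 needs last-dose dates, plus the recorded interruption dates if interruptions are to be coded.
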